## Protocol

### Background

The vast majority of the research involving dietary nitrate supplementation, namely beetroot juice, has been performed mostly on samples of healthy populations. A few clinical populations have been studied, including heart failure with preserved ejection fraction, chronic obstructive pulmonary disease (COPD), and peripheral artery disease (PAD). In various populations, beetroot juice (BRJ) has been shown to decrease overall blood pressure, increase blood flow, increase muscle tissue oxygenation, improve body core temperature regulation, and increase exercise tolerance while decreasing the oxygen cost of exercise.

BRJ supplementation has been shown to have an immediate effect on reducing blood pressure, with the most substantial decreases recorded within approximately 2.5-3 hours following supplement consumption. Systolic, diastolic, and mean arterial blood pressures showed decreases of  $10.4 \pm 3$  mmHg,  $8.1 \pm 2.1$  mmHg, and  $8.0 \pm 2.1$  mmHg, respectively, in healthy volunteers. During exercise in healthy individuals, systolic blood pressure remained lower throughout varying exercise intensities. Blood pressure was also reduced in heart failure patients with preserved ejection fraction. After an acute dose of BRJ, resting systolic blood pressure significantly decreased when compared to placebo conditions (BRJ  $127 \pm 14$  mmHg; placebo  $134 \pm 14$  mmHg). A slight reduction in systolic blood pressure during exercise may be beneficial to PAD patients. Hypertension, or high blood pressure, is a major risk factor for the development of PAD. Decreasing overall blood pressure and slightly decreasing systolic blood pressure in response to light activity would result in a decrease in unnecessary stress placed on the cardiovascular system at rest and during exercise.

In a study involving PAD patients where 7 of the 8 participants were classified as either hypertensive or prehypertensive, BRJ consumption caused a significant reduction in diastolic blood pressure during rest that was maintained during exercise testing. The study concludes that their data suggest that BRJ supplementation reduces blood pressure in PAD patients and this effect is maintained throughout exercise.

Oxygen demand of working muscle increases as activity level increases the efficiency of oxygen delivery and oxygen utilization is crucial to muscle function, as well as a necessary increase in blood flow. This is especially important in PAD patients; increasing oxygenation to areas of skeletal muscle ischemia may increase physical function. By using near-infrared spectroscopy, muscle tissue oxygenation can be examined. During cycling in healthy males supplementing with BRJ, the right vastus lateralis muscle oxyhemoglobin concentrations were greater than that of the placebo condition. While cycling at a moderate intensity, the male cyclists had a 13% reduction in deoxyhemoglobin concentration amplitude post-supplementation, which indicated a reduction in fractional oxygen extraction in the right vastus lateralis muscle. These results suggest that BRJ supplementation may promote a better balance between localized oxygen delivery and utilization as an index of muscle fractional oxygen extraction. Overall, BRJ supplementation has been shown to increase working muscle tissue oxygenation during exercise.

In PAD patients, the oxygenation of the gastrocnemius with the worst PAD symptoms was monitored during a walking cardiopulmonary exercise test. Subjects showed a 48% reduction in deoxyhemoglobin concentration amplitude following BRJ supplementation, which indicated that fractional oxygen extraction was reduced. During the exercise protocol, deoxyhemoglobin amplitude measures for the BRJ supplementation group at 100 and 200 seconds into exercise were reduced by 44% and 53%, respectively. This response implies that BRJ supplementation in PAD patients improves a balance between local oxygen delivery and utilization as an index of muscle fractional oxygenation extraction by the working muscle.

Increasing oxygenation to areas of skeletal muscle ischemia in PAD patients may increase physical function, but in order for this to be as efficient as possible, a dose-response relationship must be determined.

Increases in activity and oxygen demand of working skeletal muscle necessitate increases in blood flow. In PAD patients, increasing blood flow to working muscle becomes difficult due to atherosclerotic occlusions in the lower extremity arteries. Research in healthy populations showed significant increases in forearm blood flow during hand grip exercise in hypoxic conditions following an acute dosage of BRJ in comparison to placebo (BRJ  $373 \pm 38$  mL/min; placebo  $343 \pm 32$  mL/min). Nitric oxide signals smooth muscle within the blood vessels (endothelium) to relax, which in turn increases blood flow to the localized area of vasodilation. In healthy populations, dietary nitrate supplementation increases vasodilation near the surface of the skin. This increase in vasodilatory capacity and blood flow would create a stronger temperature gradient at the level of the skin, which would facilitate more efficient heat exchange as blood is cooled at the level of the skin (sweat evaporative, conductive, and convective cooling), causing decreased strain on the body. In PAD patients, nitrite-related nitric oxide signaling showed to increase peripheral blood flow to hypoxic tissue, which is supported by a decrease in gastrocnemius deoxygenation and a decrease in blood pressure. However, during brachial artery flow mediated dilation, peak dilation did not significantly change (BRJ  $42.6 \pm 10.6$  seconds; placebo  $41.0 \pm 10.39$  seconds), which suggested that endothelial production of nitric oxide did not change. The unchanging vasodilatory response is likely due to the study not examining a BRJ dose response relationship and its effects on vasodilation.

BRJ supplementation has been shown to decrease oxygen cost during low-intensity and moderate-intensity exercise. In trained populations supplementing with BRJ, significant decreases in oxygen cost during the beginning stages of exercise have been detected. Oxygen cost during walking was shown to decrease by approximately 12% following BRJ supplementation. BRJ supplementation showed a 20% decrease in oxygen cost during moderate intensity cycling in recreationally trained men. This reduction in oxygen cost implies an increase in exercise efficiency in light-to-moderate level exercise, which in turn increases exercise tolerance. In high-intensity exercise, time-to-exercise-failure increased by 15% following BRJ supplementation, which is also suggestive of an increase in exercise tolerance.

BRJ supplementation in clinical populations has also shown to improve exercise tolerance. In heart failure with preserved ejection fraction patients, submaximal endurance exercise improved by 24% following BRJ supplementation in comparison to placebo conditions (BRJ  $449 \pm 180$  seconds; placebo  $363 \pm 125$  seconds). In patients with COPD, walking distance increased by 11% and time to exercise fatigue increased by 6%. In PAD patients, BRJ supplementation showed an 18% (32 second) increase to onset claudication pain and a 17% (65 seconds) increase peak walking time in comparison to placebo conditions. These results in PAD patients show a substantial acute response to BRJ supplementation ( $\sim 2$  hours of consumption) during exercise testing.

In various populations, BRJ supplementation has shown to decrease blood pressure, improve blood flow, increase muscle tissue oxygenation, safely maintain core temperature, and increase exercise tolerance. The effects of BRJ specifically in PAD patients showed decreases in blood pressure, increases in time to onset claudication and exercise tolerance, but did not show a significant effect on endothelial function. Examining a dose-response relationship is necessary to determine the responses to BRJ supplementation (endothelial function, leg function, and blood vessel oxygen carrying capacity) in PAD patients. In this study, a higher dose of nitrate (280 mL, 16.8 mmol nitrates) will be examined. BRJ supplementation has shown reductions in blood pressure, increased muscle tissue oxygenation, blood flow, and thermoregulatory response. These mechanisms all contribute to improving overall cardiovascular function.

If these results are observed during this study, PAD patients may experience less claudication pain as well as better tolerance to daily physical activities and exercise.

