### Methods

Upon receiving informed consent, baseline measurements will be obtained: height/weight (standard scale and stadiometer), resting heart rate (12-lead EKG), blood pressure (automated sphygmomanometer), hand grip strength (hand grip dynamometer), body composition (handheld bioelectrical impedance analysis), blood nitrate/nitrite levels (nitrate/nitrite assay kit will quantify the amount of nitrate/nitrite in 10mL of blood), endothelial function (using flow mediated dilation), arterial stiffness (peripheral using brachial-to-ankle pulse-wave velocity analysis, central using carotid-to-femoral pulse-wave velocity analysis), autonomic function (heart rate variability measured with a heart rate monitor), leg blood flow (femoral and popliteal blood flow will be measured in both legs using a Terason uSmart 3300 ultrasound imaging system), leg muscle oxygenation (measured in the ischemic gastrocnemius using near-infrared spectroscopy), walking test (time to onset claudication using Gardner treadmill protocol), and core body temperature (rectal thermometer). The same testing procedures will occur for post-supplementation and post-placebo assessments. The initial testing visit will take 2 hours and the successive two testing visits will take 3 hours each.

After completion of baseline measurements, participants will be assigned either the beetroot juice supplement or the placebo in accordance with the prospective randomized (1:1 ratio), double-blinded, crossover study design. Supplementation dosage will be determined by mmol nitrate/kg body weight and normalized to the body mass of our participants.

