### Statistical Analysis

The statistical power analysis is reflective of a crossover experimental design. Independent t-tests, dependent t-tests, and repeated measures ANOVA will be used. Based on preliminary data of previous studies of this type, testing at the significance  $p = 0.05$ , two-tailed, will have a power of 80% to detect a difference of 0.90 standard deviations in the difference between the beetroot juice supplement group versus the placebo group. The power and sample size determination package, PASS (PASS, Number Cruncher Statistical Systems Statistical Software) was used for this analysis.

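### Does the plan need changing because a null flow-mediated dilation result at the higher dose might be inconclusive?

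*Combined protocol and SAP*

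**What the plan says.** The Background reports that, in patients with peripheral artery disease, "during brachial artery flow mediated dilation, peak dilation did not significantly change". The values are 42.6 ± 10.6 s on beetroot juice and 41.0 ± 10.39 s on placebo. It comments that "The unchanging vasodilatory response is likely due to the study not examining a BRJ dose response relationship". It later puts endothelial function first among the responses that call for dose-response work, and states: "In this study, a higher dose of nitrate (280 mL, 16.8 mmol nitrates) will be examined".

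Methods lists the measurement as "endothelial function (using flow mediated dilation", with no artery, metric or unit. The design is a 1:1 randomised, double-blind crossover of beetroot juice and placebo, with no second active dose.

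Statistical Analysis has a single power statement, "a power of 80% to detect a difference of 0.90 standard deviations in the difference", at two-sided 0.05. It names neither an outcome nor a number of participants. The only sample size given for any earlier study in this disease is in the blood-pressure part of the Background: "7 of the 8 participants were classified as either hypertensive or prehypertensive".

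**The concern.** The Background treats an earlier non-significant result as a matter of dose and does not consider imprecision. A reader may then expect this trial to settle the point, and three features suggest that it cannot.

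- There is no contrast between active doses, so a positive FMD result could not be credited to the higher dose rather than to chance or imprecision in the earlier study.
- The FMD metric is not named. The earlier result is in seconds, which is a time, so it is unclear whether the same quantity will be measured. An unnamed metric could also be chosen after the data are seen.
- An effect of 0.90 SD is large. A smaller real effect would often give a non-significant result, which might be misread as showing that raising the dose does not help.

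At stake is the interpretation of an outcome that the Background itself uses to motivate the trial.

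**Working it through.** **Inputs.** From Statistical Analysis: two-sided 0.05, 80% power, 0.90 SD of the difference. From the Background: the FMD means and ± values above, and 8 participants in a study of the same disease. Three assumptions are needed: the ± values are SDs, the FMD result came from those 8 participants, and a within-person correlation *r*, which is not given.

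**1. The plan's own figure.** For a paired t-test with *n* completers, the noncentrality is 0.90 × √*n* on *n* − 1 degrees of freedom.

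- *n* = 11: power 76.7%
- *n* = 12: power 81.0% (80.2% with *n* − 2 degrees of freedom, as in a two-period crossover analysis)

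The statement therefore implies about 12 completers. It cannot be verified further, because no number is stated.

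**2. Precision.** The 95% half-width in SD units is t(0.975, *n* − 1)/√*n*.

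- *n* = 12: 2.201/3.464 = 0.635
- *n* = 8: 2.365/2.828 = 0.836
- Ratio: 0.635/0.836 = 0.76, so the interval is 24% narrower

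A null centred on zero at *n* = 12 would exclude effects beyond about 0.64 SD. A null just short of significance would leave an upper limit near 2 × 0.635 = 1.27 SD.

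**3. Chance of missing a true effect (paired t, two-sided 0.05).**

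| True effect | *n* = 8 | *n* = 12 |
|---|---|---|
| 0.5 SD | 77% | 65% |
| 0.7 SD | 60% | 40% |
| 0.9 SD | 41% | 19% |

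The gain is modest at 0.5 SD. At the effect the trial is sized for, the risk of a miss is more than halved.

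**4. The comparison in seconds.** The earlier difference is 42.6 − 41.0 = 1.6 s. The SD of the difference is √(10.6² + 10.39² − 2*r* × 10.6 × 10.39).

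| *r* | SD of difference (s) | 0.90 SD (s) | Ratio to 1.6 s | *n* for 80% power at 3.2 s |
|---|---|---|---|---|
| 0 | 14.8 | 13.4 | 8.3 | 171 |
| 0.2 | 13.3 | 11.9 | 7.5 | 138 |
| 0.5 | 10.5 | 9.4 | 5.9 | 87 |
| 0.8 | 6.6 | 6.0 | 3.7 | 36 |
| 0.9 | 4.7 | 4.2 | 2.6 | 19 |

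These figures look alarming but carry little weight. The 1.6 s is an observed, non-significant difference, and the documents present neither it nor its double (3.2 s) as an effect worth detecting. The Background expects a larger response at the higher dose. The required *n* runs from 19 to 171 on the assumed correlation alone. The whole table also applies only if this trial measures the same quantity in seconds, which the documents do not say.

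**5. What the plan commits to.** Methods and Statistical Analysis compare beetroot juice with placebo. Neither contains a dose-response hypothesis, a comparison with the earlier study, or a rule that non-significance means no effect. The sentence about dose is background interpretation.

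**The case for a change.** The strongest case for acting is that the remedy is cheap: one line to define the metric, one to state the smallest FMD difference of interest, and one to say how a null will be read. The Background has already passed from a non-significant result to the view that endothelial nitric oxide production was unchanged, so the same misreading could recur. No primary outcome is designated, so FMD cannot be dismissed as secondary. The imprecision is also real: with 12 completers a 0.5 SD effect would be missed about 65% of the time.

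Some of this stands. The metric is unnamed, the 0.90 SD belongs to no outcome, and a non-significant FMD result from about 12 people should not be taken as evidence about the higher dose.

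The rest does not lead to a change. The missing metric is an omitted detail, and FMD is not singled out: Methods lists thirteen entries, counting height/weight as one, and the power statement is tied to none of them. A sample-size justification and a null-reading rule for this measure alone would be a matter of preference. Raising the sample size would answer a question the plan does not pose, and no stated figure is missed. Limiting conclusions to the study dose would forbid a claim the plan never makes.

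**Conclusion.** No change to the plan follows. Beetroot juice versus placebo at the study dose is a sound comparison, and the dose explanation in the Background is motivation, not a hypothesis under test. The unnamed FMD metric is a gap that competent analysts fill by fixing the metric and unit before unblinding and reporting the beetroot-minus-placebo difference with its 95% confidence interval. That interval would itself show how much a null leaves open.

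On the implied 12 completers, the half-width is about 0.64 SD of the difference, against 0.84 SD with 8. To call a null here nearly as inconclusive as the earlier one is too strong: the miss rate at 0.90 SD falls from 41% to 19%. The comparison rests on two sample sizes that the documents do not state. The 12 is solved from the power statement, and the 8 is borrowed from the blood-pressure part of the Background. If this trial had 20 paired completers, the half-width would be 2.093/√20 = 0.47 SD, 44% narrower than with 8. The seconds-based figures rest further on an unknown correlation, on the ± values being SDs, and on the metric being the same, so they support no conclusion about adequacy.

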### Methods

Upon receiving informed consent, baseline measurements will be obtained: height/weight (standard scale and stadiometer), resting heart rate (12-lead EKG), blood pressure (automated sphygmomanometer), hand grip strength (hand grip dynamometer), body composition (handheld bioelectrical impedance analysis), blood nitrate/nitrite levels (nitrate/nitrite assay kit will quantify the amount of nitrate/nitrite in 10mL of blood), endothelial function (using flow mediated dilation), arterial stiffness (peripheral using brachial-to-ankle pulse-wave velocity analysis, central using carotid-to-femoral pulse-wave velocity analysis), autonomic function (heart rate variability measured with a heart rate monitor), leg blood flow (femoral and popliteal blood flow will be measured in both legs using a Terason uSmart 3300 ultrasound imaging system), leg muscle oxygenation (measured in the ischemic gastrocnemius using near-infrared spectroscopy), walking test (time to onset claudication using Gardner treadmill protocol), and core body temperature (rectal thermometer). The same testing procedures will occur for post-supplementation and post-placebo assessments. The initial testing visit will take 2 hours and the successive two testing visits will take 3 hours each.

After completion of baseline measurements, participants will be assigned either the beetroot juice supplement or the placebo in accordance with the prospective randomized (1:1 ratio), double-blinded, crossover study design. Supplementation dosage will be determined by mmol nitrate/kg body weight and normalized to the body mass of our participants.

### Statistical Analysis

The statistical power analysis is reflective of a crossover experimental design. Independent t-tests, dependent t-tests, and repeated measures ANOVA will be used. Based on preliminary data of previous studies of this type, testing at the significance  $p = 0.05$ , two-tailed, will have a power of 80% to detect a difference of 0.90 standard deviations in the difference between the beetroot juice supplement group versus the placebo group. The power and sample size determination package, PASS (PASS, Number Cruncher Statistical Systems Statistical Software) was used for this analysis.

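### None of the tests listed for this two-period crossover is said to adjust the beetroot–placebo comparison for period; a period-adjusted within-participant estimate would cost under 1 point of power with equal sequences

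*Combined protocol and SAP*

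**What the plan says.** The Methods section describes a "prospective randomized (1:1 ratio), double-blinded, crossover study design". Participants have a baseline assessment and are then tested twice more: "The initial testing visit will take 2 hours and the successive two testing visits will take 3 hours each". On content, "The same testing procedures will occur for post-supplementation and post-placebo assessments". Each participant therefore contributes one post-beetroot and one post-placebo value per outcome, and each value belongs to the first or the second test period.

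The Statistical Analysis section has one sentence on method: "Independent t-tests, dependent t-tests, and repeated measures ANOVA will be used". It ties no test to a comparison or an outcome, and neither period nor sequence is mentioned. On power it says "The statistical power analysis is reflective of a crossover experimental design" and gives a "power of 80% to detect a difference of 0.90 standard deviations in the difference between the beetroot juice supplement group versus the placebo group", two-tailed at 0.05. The available text states no sample size.

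**The concern.** In a two-period crossover, a participant's beetroot-minus-placebo difference contains the treatment effect plus or minus any change between the first and second test visits. The sign depends on the order received. With repeated treadmill testing and vascular measurements, a change from one visit to the next is possible, although the documents document none.

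A paired test that ignores order treats this change as noise. If the two orders have equal numbers, the change cancels from the mean but inflates the standard deviation, so power falls. If the numbers are unequal, it no longer cancels and part of it is read as treatment effect. A period term removes both problems. None of the three listed tests is said to carry one, and the plan does not say which of them gives the treatment comparison.

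**Working it through.** **Inputs.** From the Statistical Analysis section: two-sided alpha 0.05, power 80%, effect 0.90 SD. Assumed: the SD is that of the within-participant difference (set to 1); the period shift *s* is the change from first to second test visit in units of that SD; sequence splits are 6/6, 5/7 and 4/8; there is no carryover.

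**1. Implied sample size.** The stated 80% cannot be reproduced directly because no N is given, so N is solved for. The normal approximation gives ((1.960 + 0.842)/0.90)² = 9.7, or 10. The noncentral t (noncentrality 0.90√n, df n − 1) gives 76.7% at n = 11 and 81.0% at n = 12. N = 12 is used below.

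**2. Paired test without period, 6/6.** Differences centre on 0.90 − s in one sequence and 0.90 + s in the other. Their mean is still 0.90, but the expected sample variance becomes 1 + 12s²/11:
- s = 0.25: 1.068 (SD 1.03)
- s = 0.5: 1.273 (SD 1.13)
- s = 1: 2.091 (SD 1.45)

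Simulated power at s = 0, 0.25, 0.5 and 1 is 81.0%, 79.1%, 73.2% and 49.7%. The period-adjusted test stays between 80.1% and 80.3%.

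**3. Unequal sequences.** Given the split, the error in the unadjusted estimate is s × (n2 − n1)/N. For s = 0.5:
- 5/7: 0.5 × 2/12 = 0.083 SD
- 4/8: 0.5 × 4/12 = 0.167 SD

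Set against 0.90, these are 9% and 19%. The sign depends on which sequence is larger and on the direction of the shift. Simulated means with the error downward are 0.817 and 0.733. At 4/8, unadjusted power is then 55.0%, or 87.6% with the error upward; the adjusted test has 75.5% either way.

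**4. Cost of adjusting when there is no shift.** The adjusted estimate is the average of the two sequence means of beetroot minus placebo, with SE = √((1/n1 + 1/n2)/4) and df N − 2.
- 6/6: SE 0.2887, noncentrality 0.90/0.2887 = 3.118, power 80.2%
- 5/7: SE 0.2928, noncentrality 3.074, power 79.1%
- 4/8: SE 0.3062, noncentrality 2.939, power 75.5%

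The unadjusted paired test has 81.0%.

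**5. False positives.** With s = 0.5 and no treatment effect, the unadjusted paired test rejects in about 2.9% (6/6), 3.6% (5/7) and 5.6% (4/8) of simulated trials.

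**The case against.** The strongest reply is that the plan already points to a paired analysis. It ties the power calculation to a crossover, expresses the effect in standard deviations of a difference, and lists dependent t-tests. That is accepted: a paired comparison is the natural reading, and what remains is the absent period term.

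A reader might instead infer from the first listed test that post-beetroot and post-placebo values will be compared as separate groups. The text does not say so. An independent t-test is legitimate in a crossover when it compares period differences between sequences, which is the analysis recommended here. Unpaired power of 73%, 58% and 31% at correlations 0.3, 0.5 and 0.7 applies only if a trial sized for a paired test (12 participants) is analysed unpaired. If 0.90 were a between-participant SD and the trial were sized for an unpaired test (21 per condition, 81.2%), an unpaired test on crossover data would have about 81%, 85%, 89% and 93% power at correlations 0, 0.3, 0.5 and 0.7, so the planned power would not be lost.

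It can also be said that repeated measures ANOVA could include period. It could, but the plan names no factors, and an ANOVA over baseline, beetroot and placebo has no period term unless one is added.

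Finally, the loss is conditional. No shift is documented, a 0.25 SD shift costs about 2 points at 6/6, and adjusting costs 5.5 points at 4/8 when there is no shift. All of this stands, and it limits the weight of the point.

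**Conclusion.** The point holds as a cheap improvement that should be made: no listed analysis is said to adjust the beetroot–placebo comparison for period. On the paired reading with 12 participants, omitting period costs about 2, 8 and 31 points of power at shifts of 0.25, 0.5 and 1 SD with a 6/6 split. With a 0.5 SD shift it also displaces the estimate by 0.083 SD at 5/7 and 0.167 SD at 4/8.

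The absence of the wording is certain in the available text. The sizes are not, because N, the split and the shift are assumed. The adjusted estimate is free of the period shift, but it is unbiased only without carryover, which the Methods and Statistical Analysis sections do not address.

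Two stronger readings are not supported. The plan does not commit to an unpaired comparison of the two conditions. Nor is there a material false-positive problem: the highest null rejection rate found with a 0.5 SD shift was about 5.6%. The unstated N and the meaning of the 0.90 SD are missing detail and carry no weight in this conclusion.

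**What to change.** In the Statistical Analysis section, state that for each outcome measured at both post-intervention visits, beetroot minus placebo will be estimated within participant, adjusted for period, with a 95% confidence interval. Then give each listed test a role:

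- **Independent t-test:** a two-sample comparison of period differences (first minus second test visit) between the two sequences. Half the difference in means is the treatment effect. It may also describe the sequence groups at baseline. Do not use it to compare post-beetroot with post-placebo values as separate groups.
- **Mixed model, as an alternative:** treatment, period and sequence fixed, participant random. With complete data it gives the same result when the estimated participant variance is positive; the t-test does not depend on that condition.
- **Dependent t-test:** replaced as the treatment comparison.
- **Repeated measures ANOVA:** limited to a model with a period term, or to a descriptive comparison of the three occasions.

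For leg blood flow, which is measured in both legs, use one prespecified value per participant per visit or add leg to the model. The single baseline is common to both conditions and cancels from the difference, so it need not enter the model. State that the estimate assumes no carryover.

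The cost is wording only, with no extra data or participants. The adjustment uses one residual degree of freedom, plus some precision if the sequences are unequal. At N = 12 with no period shift, that is a loss of 0.8 points at 6/6, 1.9 at 5/7 and 5.5 at 4/8. Keeping sequence numbers equal holds it under 1 point.

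### The plan ties no listed test to the two-period crossover comparison and names no period term; stating a period-adjusted within-person estimate is a cheap safeguard.

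*Combined protocol and SAP*

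**What the plan says.** The Methods section describes a "prospective randomized (1:1 ratio), double-blinded, crossover study design". There is one baseline visit and then two treatment visits: "The initial testing visit will take 2 hours and the successive two testing visits will take 3 hours each". The measurements are repeated unchanged at each: "The same testing procedures will occur for post-supplementation and post-placebo assessments". They include a "walking test (time to onset claudication using Gardner treadmill protocol"). The whole battery is therefore run once before treatment is given: "After completion of baseline measurements, participants will be assigned either the beetroot juice supplement or the placebo".

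The Statistical Analysis section states the methods in one sentence: "Independent t-tests, dependent t-tests, and repeated measures ANOVA will be used". It attaches none of them to the beetroot-placebo comparison and lists no factors for the ANOVA. Period, sequence and carryover are not mentioned in either section. The power statement is two-sided at 0.05, with 80% power to "detect a difference of 0.90 standard deviations in the difference between the beetroot juice supplement group versus the placebo group". No sample size is given.

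**The concern.** In a two-period crossover, each participant's beetroot-minus-placebo difference contains the treatment effect plus or minus any average change from the first treatment visit to the second. The sign depends on which treatment came first. A plain dependent t-test pools the two sequences and ignores this, with two consequences:

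- **Equal sequences.** The shift cancels from the mean but spreads the differences apart. The estimate stays unbiased, the interval widens, and the test becomes conservative. The loss is power, not validity.
- **Unequal sequences.** The shift no longer cancels. The estimate is biased, towards or away from beetroot depending on which sequence is larger and which way the shift runs.

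The dependent t-test is one of the listed methods, and nothing in the text rules it out as the main comparison. In a small trial, one or two dropouts are enough to unbalance the sequences.

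**Working it through.** **Inputs from the Statistical Analysis section.** Two-sided 0.05; 80% power; effect of 0.90 SD, read here as SD of the within-person difference because the power statement is said to reflect a crossover.

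**Assumptions (not in the documents).** N; the split between sequences; the period shift π, defined as the mean change from first to second treatment visit in SDs of the within-person difference.

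**Step 1: the N implied by 80% power.** The stated power cannot be reproduced directly without N, so solve for N. For a paired t-test (noncentral t, noncentrality 0.90√N, N − 1 df), N = 11 gives 76.7% and N = 12 gives 81.0%. Take N = 12.

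**Step 2: the period-adjusted analysis.** The estimate is the average of the two sequence-specific mean differences. Its SE is 0.5·√(1/n₁ + 1/n₂), on n₁ + n₂ − 2 = 10 df. It does not depend on π.

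- 6 v 6: SE 0.289, noncentrality 0.90/0.289 = 3.12, power 80.2%
- 7 v 5: SE 0.293, noncentrality 3.07, power 79.1%
- 8 v 4: SE 0.306, noncentrality 2.94, power 75.5%

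With no period effect the plain paired test has 81.0% at any split. The cost of adjusting is therefore 0.8, 1.9 and 5.5 points respectively.

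**Step 3: the plain paired test under a shift, 6 v 6.** The sequence means are 0.90 ± π. Results are by simulation (400,000 runs).

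| Shift π (SD) | Power, unadjusted | Power, adjusted | Type I error, unadjusted | Mean 95% half-width, unadjusted (adjusted 0.63) |
|---|---|---|---|---|
| 0 | 81.0% | 80.2% | 5.0% | 0.62 |
| 0.15 | 80.3% | 80.2% | – | – |
| 0.25 | 79.0% | 80.2% | 4.4% | 0.64 |
| 0.5 | 73% | 80.2% | 3.0% | 0.70 |
| 0.75 | 63% | 80.2% | 1.6% | 0.79 |

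Break-even is at about 0.15 SD. The gain from adjusting is about 1 point at 0.25 SD (80.2 − 79.0) and about 7 points at 0.5 SD (80.2 − 73).

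**Step 4: unequal sequences.** Bias of the unadjusted estimate = π(n₁ − n₂)/N.

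- 7 v 5: π × 2/12 = π/6, which is 0.042 SD at π = 0.25 and 0.083 SD at π = 0.5.
- 8 v 4: π × 4/12 = π/3, which is 0.083 SD at π = 0.25 and 0.167 SD at π = 0.5.

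At 7 v 5 and π = 0.5, unadjusted power is 64% if the bias opposes beetroot and 81% if it favours it, against 79% adjusted. The 81% reflects an overstated effect. At π = 0.25 the figures are 75% and 83% against 79%. Type I error is still below 5% at 7 v 5 (about 3.6% at π = 0.5). At 8 v 4 it is slightly above, at about 5.6%.

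**Step 5: the other reading of 0.90 SD.** If it is the SD of single measurements with no within-person correlation, the paired effect is 0.90/√2 = 0.636 SD and N = 22. Unadjusted power is then 81.2%, 79.4% and 73.8% at shifts of 0, 0.25 and 0.5, against 81.0% adjusted. The pattern is unchanged.

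**The case against.** **The harm is conditional.** A reader might infer from the sentence on methods that the trial will ignore period. The text does not support that. An independent t-test on period differences between sequences is a period-adjusted crossover analysis, and so is a repeated measures ANOVA with a period factor; both tests are on the list. What stands is a gap in specification.

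**False positives are not the issue.** A reader might also infer that type I error is inflated. With equal sequences the unadjusted test is conservative, and even at 8 v 4 the excess is about half a point.

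**The period effect is assumed.** No figure in the documents gives or implies one. Because the treadmill test and the rest of the battery are run at baseline, part of any practice effect falls outside the beetroot-placebo contrast. That makes the 0.5 and 0.75 SD rows less plausible. At 0.25 SD the gain is about 1 point of power, and below about 0.15 SD adjusting loses a little. This stands and limits the claim.

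**The fix is not free under imbalance.** Methods does not say how the 1:1 ratio is enforced. If allocation were simple and unblocked (an assumption), a split of 8 v 4 or worse at N = 12 has probability 2 × 794/4096, about 39%. With no period effect, 8 v 4 costs 5.5 points. This stands too, but it argues for balanced allocation rather than for the unadjusted test, whose estimate at 8 v 4 is biased by a third of any shift.

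**Seconds are illustration only.** One could equate 0.90 SD with the "18% (32 second) increase to onset claudication pain" cited in Background, which puts break-even at 0.15 × 32/0.90, about 5 seconds. The power statement does not link 0.90 SD to walking time or to any other outcome, so this carries no weight.

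**No primary outcome is named.** A sentence about a single main estimate would leave open which measure it governs. The fix is therefore worded for each outcome.

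**Conclusion.** The point holds as a cheap improvement, not as a demonstrated error. The plan leaves the main crossover comparison open, and one listed method, taken literally, would ignore period. The size of the benefit is unknown because it depends on a period effect that the documents do not give. At the assumed N of 12 and equal sequences it runs from a loss of 0.8 points of power with no shift to a gain of about 7 points at 0.5 SD, and the upper part of that range is the less likely. The protection against bias matters only if the sequences end unequal and a shift exists. The conclusion rests on the back-solved N, on 0.90 SD referring to within-person differences (N = 22 gives the same pattern), and on the illustrative shifts. Adjusting for period does nothing about carryover.

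**What to change.** Add to Statistical Analysis: for each outcome, the beetroot-placebo estimate is the within-person difference adjusted for period. Obtain it in either of two ways:

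- compare the period differences (first minus second treatment visit) between the two randomised sequences with an independent t-test, and halve the difference between sequences and its interval; or
- fit a repeated-measures model with treatment, period and participant.

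Both are within the methods already listed. State in Methods that allocation to sequence is kept balanced, for example by small blocks, since the price of adjusting grows with imbalance.

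The change needs no new visits, samples or participants. It uses one degree of freedom, and the power given up when there is no period effect is as worked out above: under 1 point with equal sequences.
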